4. OBJECTIVES AND OUTCOME MEASURES/ENDPOINTS

	Objectives	Outcome Measures
Primary	To develop and pilot test a novel MR imaging protocol with the aim to accurately: 1. Quantify tumour burden 2. Quantify bone loss	Novel imaging based endpoints: 1. DW-MRI: ADC change (Pawlyn et al, 2016) 2. Total spinal 'hole' volume 3. Total spine 'collapse' volume 4. FSA: trabecular wall thickness (Rafferty et al, 2016) Correlate endpoints: Bone density (DXA imaging) Serum CTX-1 Serum P1NP Further experimental serum biomarkers of myeloma bone disease
Secondary	To pilot test a novel MR imaging protocol with the aim to accurately: 1. Detect longitudinal changes in tumour load with therapy 2. Detect longitudinal changes in bone	1 and 2 - Repeat quantification of endpoint parameters after induction therapy and best response achieved by IWMG criteria or at treatment failure

microarchitecture with	3 – Analyse participants quality of
therapy	life using data from the EQ-5D-5L
3. Assess participants	questionnaire
Quality of Life (EQ-5D)	
throughout the study	
4. Assess participants experience of the novel MR imaging scan	4- Analyse participants experience of the novel MR imaging using data from MRI/DXA scanning questionnaire

5. STUDY DESIGN

This novel MR protocol is developing new metrics and combining elements that have not previously been combined therefore, there will be a protocol development phase prior to trial recruitment in which a group of healthy volunteers will be scanned to ensure timings and data collection is optimized. This phase will take place prior to trial start and is not included as part of this protocol, as it is already covered by REC approval for OCMR protocol development.

Once the protocol development phase has been completed, 60 subjects will be recruited to take part in this study; Group 1: Myeloma, (n=34), Group 2: MGUS, (n=13) and Group 3: Healthy age-matched volunteers, (n=13). Participants from Groups 1 and 2 will be identified and approached by a healthcare professional in the oncology clinic at the Churchill Hospital, Oxford. Group 3 participants will usually be the partners of the participants from group 1 and 2, and they will be recruited alongside the participants in Groups 1 and 2.

As participants in Groups 1 and 2 will be recruited at the point of either diagnosis or relapse, any standard investigations their clinician deems necessary for their diagnostic evaluation within NHS protocols will also be performed. Following recruitment, all participants (Groups 1-3) will undergo the first study appointment, the experimental combined MR imaging protocol. Alongside this, participants in Groups 1 and 2 only will undergo the DXA imaging scan and the bone biomarker blood and urine tests. Once both imaging appointments have been completed, all participants will be asked to complete a short questionnaire relating to the MRI imaging and Groups 1 and 2 will be asked to complete this questionnaire for the DXA imaging too; no questionnaires are to be completed for the bone biomarker test. Groups 1 and 2 participants will also be asked to complete a validated quality of life questionnaire.

Participants in Groups 1 and 2 will undergo a further experimental MR scan, DXA imaging and bone biomarker blood tests at 6 months or at time of progression/relapse, whichever is sooner (but no sooner than 3 months after the initial investigations) to evaluate change in disease burden and bone loss. The reason participants in Group 2 will be rescanned at 6 months even if they have not progressed to myeloma and are not on therapy, is to address the following questions, 1. Can trabecular thinning progression be detected with time in MGUS patients whose paraprotein is stable or rising? 2. Reproducibility test: In

patients with a stable paraprotein, if assumed that trabecular thickness is stable or at most slightly worse over 6 months, is trabecular quantification reproducible over time?

In addition to this, all participants in Groups 1 and 2 will also be asked to complete the short questionnaire relating to the MRI and DXA imaging and the quality of life questionnaire for assessment of patient experiences of both imaging procedures, both at the first study appointment and at the 6 month follow up appointment. Standard of care clinical investigations will be repeated within NHS protocols if clinically indicated. Results of relevant NHS diagnostic investigations, clinical outcomes and survival data will be collected and stored.

6. PARTICIPANT IDENTIFICATION

6.1. Study Participants

Patients with newly diagnosed or relapsed myeloma, smouldering myeloma (Group 1; n=34), MGUS (intermediate or high risk) (Group 2; n= 13), and healthy age-matched volunteers (Group 3; n=13) are eligible to be included in the trial if they meet the following criteria:

6.2. Inclusion Criteria

Inclusion Criteria (All Groups)

- Participant is able to and willing give informed consent for participation in the study.
- Male or Female, aged 18 years or above.

Inclusion Criteria (Groups 1 and 2)

- Newly diagnosed myeloma or newly- relapsed myeloma eligible for next therapy,
- Smouldering myeloma or intermediate or high risk MGUS
- Patients attending Oxford NHS Haematology-oncology centre
- Diagnoses of MGUS, Smouldering Myeloma and MM- made in accordance with the clinical diagnostic criteria set forth by IMWG (International Myeloma Working Group)

6.3. Exclusion Criteria

Exclusion Criteria (All Groups)

Those who are unable or unwilling to give informed consent

Women who may be pregnant, breast feeding or women of child-bearing potential who are unwilling
or unable to take sufficient precautionary measures will be excluded due to DXA imaging.

Exclusion Criteria (Groups 1 and 2)

- Signs of Spinal Cord Compression
- Patients with documented metastatic lesions from another type of malignancy
- Known contraindication for a MRI scan (see Appendix B: contraindications to MR scan), including unacceptable pain on lying flat for 1 hour.

7. STUDY PROCEDURES

Summary: In order to pilot test a novel MRI imaging protocol, this study will compare current, NHS-available myeloma tumour and bone disease assessment tools, with the novel MR imaging technique. Blood sampling for bone turnover biomarkers, DXA imaging and the novel MR scan will be performed in addition to any standard NHS tests deemed necessary by clinical care team. Three groups of participants will be included, Group 1 (Myeloma), Group 2 (MGUS) and Group 3 (Healthy Volunteers). Group 3 will only receive a single MR scan with no further investigations whereas Groups 1 and 2 will go onto receive DXA scan and blood tests. Relevant baseline information including medical history, prior course of disease and use of bone modifying therapy will be recorded at start of study for Groups 1 and 2, and once more at 6 months post-recruitment, or at relapse/progression if sooner.

7.1. Recruitment

Newly diagnosed or newly relapsed myeloma patients (Group 1) with or without X-ray detectable bone disease, Smouldering myeloma and high or intermediate MGUS patients (Group 2), without X-ray detectable bone disease, will be invited to participate. Healthy age-matched volunteers (Group 3) will be recruited from the local myeloma support group community, (for example patients' partners).

Patients will be identified by the clinician or clinical care team. Potential patients will then be approached by the myeloma clinical research team during a routine clinic visit and given information about the study. If the participant is interested then they will have a further detailed discussion about the study with a research coordinator and will be given the participant information sheet to take home. They will return to clinic after a minimum period of 24 hours, and will have the opportunity to ask any questions regarding the study. If the participant remains happy to enter the study, their informed consent will be obtained by the investigator prior to initiating any study related investigations.

We anticipate a 10% screen failure for group 1 participants, primarily due to pain and contraindications for MRI. We anticipate 5% screen failure rate for group 2 participants due to contraindications for MRI scan. Both of these figures have been incorporated in the sample size calculations.

7.2. Informed Consent

Informed consent will be taken at a routine clinic visit. The participant must personally sign and date the latest approved version of the Informed Consent form before any study specific procedures are performed.

Copies of the Participant Information Sheet and Informed Consent will be presented to the participants detailing no less than: the exact nature of the study; what it will involve for the participant; the implications and constraints of the protocol; the known side effects and any risks involved in taking part. It will be clearly stated that the participant is free to withdraw from the study at any time for any reason without prejudice to future care, without affecting their legal rights, and with no obligation to give the reason for withdrawal. A member of the clinical team will talk through the PIS with the participant before Informed Consent is obtained.

The participant will be allowed as much time as wished to consider the information, and the opportunity to question the Investigator, their GP or other independent parties to decide whether they will participate in the study. Written Informed Consent will then be obtained by means of participant dated signature and dated signature of the person who presented and obtained the Informed Consent. The person who obtained the consent must be suitably qualified and experienced, and have been authorised to do so by the Chief Investigator. A copy of the signed Informed Consent will be given to the participant. The original signed form will be retained at the study site.

Those who have not communicated a decision regarding consent may be re-approached on one occasion after 2 months by the local research team.

7.3. Screening and Eligibility Assessment

7.3.1 Screening Logs

The research team will be expected to maintain a screening log of all potential participants. Participants will not be registered at consent and therefore during screening, potential participants should be identified by limited information only; this should include initials, date of birth, screening date and outcome of the screening process (e.g. enrolled into study, reason for ineligibility if known, or refused to participate). Screening logs will be filed in the trial master file.

7.3.2 Screening Assessments

All screening study assessments must be completed before any study procedures are carried out.

The following assessments will be carried out in order to establish eligibility for the study for participants in Groups 1 and 2 only.

Medical History

Detailed history of myeloma/MGUS including; date of diagnosis, staging (International Staging System) and location(s) of bone disease as per standard of care should be recorded. Detailed description of all prior and ongoing diseases and disorders should be documented along with any myeloma or bone strengthening therapies that were received.

Particular Details on history of fractures, history of osteoporosis, bone pain and analgesia requirements should be documented. Details on use of radiotherapy or vertebral augmentation should be collected.

- Treatment History and Concomitant Medication(s)
 Details of treatment history and current concomitant medication including all medications,
 treatments and therapies used in the prior 4 weeks, as well as those currently being taken should be recorded.
- Physical Examination
 Physical examination including assessment of ECOG status (Group 1 only), height and weight should
 be recorded for all participants.
- Local Clinical Laboratory Evaluations
 - Biochemistry: Sodium, Potassium, Total Protein, Albumin, Adjusted Calcium, Bicarbonate, Magnesium, Phosphate, Urea, Creatinine, LFTs, CRP, LDH, Uric acid, Glucose, Creatinine Clearance
 - Immunology: Beta-2 microglobulin, paraprotein, quantitative immunoglobulins, serum free light chains
 - Haematology: haemoglobin, haematocrit, bilirubin, WBC, platelet count, neutrophils, lymphocytes
 - Bone marrow assessment (only Myeloma and Smouldering myeloma): bone marrow aspirate and trephine to confirm diagnosis of myeloma
 - Urine pregnancy test: for women of child bearing potential (WCP)

Participants in Group 3 will undergo the following screening assessments before any study procedures are carried out:

- Medical History
 - Detailed history of any relevant previous medical conditions and their treatments
- Physical Examination
 Physical examination of height and weight to be recorded

7.3.3 Recruitment Logs

Participants deemed eligible after screening will be registered on to the study and be given a unique Study ID. Registered participants will be recorded on an enrolment log with information including Study ID, Date of Birth, Initials and hospital number as well as date of consent. No personal information, which may identify the participant, should be included on the recruitment log.

7.3.4 Participant Trial Card

After a participant has been enrolled onto the study, the research staff should inform the participant of their Study ID and provide a completed Participant Trial Card including details of dates of the scans and staff contact details.

7.4. Baseline Assessments

7. 4.1 Baseline Assessments for Groups 1 and Group 2

Once consent has been given, the first study appointment will be offered, within four weeks. This first study visit will include the MR imaging protocol, DXA scanning, bone biomarker blood/urine tests and completion of both questionnaires. These procedures are described in further detail below. An administrator will manage these attendance arrangements; however, participants will be required to make arrangements for transportation to and from the OCMR and NOC. Participants will be given the opportunity to claim back the travel expenses and details of how to do this is available in the Participant Information Sheet. Whenever possible, the administrator will try and arrange for the MRI and DXA scan to happen on the same day, should this not be possible and the scans are arranged for different days, the participants will have to attend an additional study visit.

- Blood and urine samples for bone turnover biomarkers total ALP, PINP and serum CTX1 (Vasikaran et al, 2011). This will require a morning fasted 20ml clotted (serum) blood sample to be taken. Additional experimental assays of biomarkers for myeloma bone disease will be performed on these samples at the Oxford University Hospitals NHS Foundation trust laboratory. This assessment will take approximately 10 minutes.
- 2. Body composition using whole body DXA (1 hour radiology appointment at the NOC (Nuffield Orthopaedic Centre)). Bone Mineral Density (BMD) will be measured by (DXA) using a study approved densitometer. BMD measurements will be made at the lumbar spine (L1-4), hip, whole body and an Instant Vertebral Assessment (IVA). If participants have already had a DXA scan at one of these sites within 2 months of the visit date, then that scan will be used and the scan will not be repeated for that site. This assessment will take approximately 50 minutes.
- 3. Experimental MR imaging protocol (1 hour radiology appointment). MRI scans will be performed in a 60-minute protocol on the 1.5T or 3T Avanto MRI scanner (Siemens, Germany) installed at OCMR (Oxford Centre for Magnetic Resonance), John Radcliffe Hospital, [name]. Scans will include: localizer images, high-resolution 3D imaging of the pelvis and lumbar spine, diffusion-weighted MRI imaging following the method described for use in myeloma patients by Giles *et al* (Giles *et al*, 2015; Giles *et al*, 2014; Pawlyn *et al*, 2016), and an experimental bone density quantification MR method based on published techniques (Evans *et al*, 2014; Rafferty *et al*, 2016), using software from Osteotronix Ltd, in the pelvis and two sites in the lumbar spine. Blinded data gathered from experimental MRs will be used to generate disease burden in percentage marrow infiltration, high-resolution 3D imaging-generated total spinal lytic and collapse volumes, and bone structure quantification. Marrow infiltration will be correlated with marrow infiltration data as determined by bone marrow biopsy (and PET-CT scans where performed). MR-generated bone density quantification and total spinal lytic and collapse volumes will be correlated with bone mineral density as estimated by DXA scan. As there is no

accepted "gold standard" method for quantifying myeloma-associated bone loss against which to compare, in all the healthy volunteers and in 10 myeloma patients who are tolerating the procedure without problem and who are willing repeat MR bone density measurements will be performed (a subsection of the whole protocol, lasting max. 15 minutes) within each attendance, to assess reproducibility.

4. At the end of both the experimental MR and the DXA scan, all participants will be asked to complete the Quality of Life Questionnaire and the novel MR experience questionnaire. This assessment will take approximately 15 minutes.

See Appendix A for time frame of assessments.

No contrast medium will be used.

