3. BACKGROUND AND RATIONALE

Multiple myeloma, a malignancy of monoclonal B-cells, is the second most common haematological malignancy, compromising of 2% of all cancers in the UK and is currently incurable. At diagnosis and each relapse, treatment of myeloma consists of conventional chemotherapy combined with novel agents. In those fit enough, autologous (and in some cases allogeneic) stem cell transplantation is used to prolong remissions (NICE, 2016). A number of tests are used for disease quantification to guide therapy; however these tests each have limiting factors. Bone marrow histology using a bone marrow biopsy is painful and invasive; it also cannot predict global myeloma infiltration, which is not uniform and varies through the skeleton, and no bone loss information can be obtained. Serum paraprotein, light or heavy chain quantification must be used for regular monitoring; however this fails in non-paraprotein secreting myelomas, and although it tracks the secretory capacity of a plasma cell clone, that feature can change over the course of the disease.

PET-CT (positron emission tomography- computed tomography) is the imaging gold standard in myeloma for quantifying total disease burden (Cavo *et al*, 2017). This cannot however quantify bone loss, either microarchitecture changes or lytic lesions. It therefore cannot be used to track response to anti-bone-resorptive therapies.

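### MR and biopsy percentage marrow infiltration are compared by correlation only, which cannot support the aim to quantify tumour burden accurately; add an agreement analysis read in light of biopsy sampling error

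*Combined protocol and SAP*

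**What the plan says.** Section 4 gives the primary objective as "To develop and pilot test a novel MR imaging protocol with the aim to accurately: 1. Quantify tumour burden", followed by bone loss. For tumour burden the listed endpoint is ADC change.

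Section 7.4.1 adds a derived measure: "Blinded data gathered from experimental MRs will be used to generate disease burden in percentage marrow infiltration". The comparison planned for it is one sentence: "Marrow infiltration will be correlated with marrow infiltration data as determined by bone marrow biopsy". PET-CT, where performed, is a second comparator in the same sentence and by the same method.

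Section 10.2 does not mention the biopsy comparison. Its correlations are of ADC, hole and collapse volumes and FSA with DXA bone mineral density, CTX-1 and P1NP. Its other analyses are a paired t test of change, ANOVA and ANCOVA between groups, a regression of EQ-5D and a descriptive questionnaire summary. No bias estimate, limits of agreement, concordance coefficient or calibration appears anywhere.

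Three further statements bear on the point:

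- Section 3 says of biopsy that "it also cannot predict global myeloma infiltration, which is not uniform and varies through the skeleton".
- Section 7.3.2 restricts who has a marrow sample: "Bone marrow assessment (only Myeloma and Smouldering myeloma): bone marrow aspirate and trephine to confirm diagnosis of myeloma".
- The within-visit repeats in section 7.4.1 concern bone density: "repeat MR bone density measurements will be performed (a subsection of the whole protocol, lasting max. 15 minutes) within each attendance, to assess reproducibility". They do not cover marrow infiltration.

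**The concern.** MR infiltration and biopsy infiltration are both percentages of marrow involvement, so they can be set against each other in percentage points. Correlation discards that information. It shows whether patients with higher biopsy values tend to have higher MR values. It does not show whether the MR value is close to the biopsy value. It also rises with the spread of disease in the sample, and Group 1 mixes smouldering, newly diagnosed and relapsed disease.

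A shift in the MR scale is not far-fetched. Section 3 notes that ADC depends on scanner manufacturer and field strength, and section 7.4.1 allows scanning at 1.5T or 3T.

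At stake is what the pilot can say about its tumour-burden aim. A high r could sit beside a large systematic difference between MR and biopsy, and nothing in the plan would bring that difference to light.

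**Working it through.** **The plan's own figure.** The only sample size in the document is 34 (29 vs 5), in section 10.1, for ADC by response: difference 0.75, SD 0.5, ratio 0.15, 80% power, alpha 0.05 (two-sided assumed).

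- Normal approximation: n1 = (1 + 1/0.15) × (0.5 × 2.80/0.75)² = 26.7, so 27. Then n2 = 0.15 × 26.7 = 4.01, so 5. The total is 32.
- A noncentral t calculation gives 85% power at 29 vs 5.
- The stated 34 is therefore consistent with its inputs. It was not derived for the MR-biopsy comparison, which has no sample size.

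**Invariance of r.** For y = a + b·x with b > 0, corr(x, a + b·x) = 1 for any a and b. Adding random error before the shift or rescaling lowers r by the same amount whatever a and b are. Take section 10.1's burden of 40% falling to 10%:

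| MR error | 40% reads | 10% reads | Apparent fall | r |
|---|---|---|---|---|
| none | 40 | 10 | 30 points | unchanged |
| +20 points | 60 | 30 | 30 points | unchanged |
| reads half | 20 | 5 | 15 points | unchanged |

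Halving understates the fall by half (15 instead of 30 points).

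**With random error.** Assumptions not in the document: biopsy SD 15 points (range 10 to 20) and random MR error SD 7 points. The mean of 40% is from section 10.1. For this illustration biopsy is treated as free of error.

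- r = 15/√(15² + 7²) = 15/16.55 = 0.906 in every row below.
- Lin's concordance = 2·cov/(var_x + var_y + bias²).

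| MR error | r | Concordance | Bias | 95% limits of agreement |
|---|---|---|---|---|
| none | 0.906 | 450/(225 + 274) = 0.90 | 0 | −13.7 to +13.7 |
| +20 points | 0.906 | 450/(225 + 274 + 400) = 0.50 | +20 | +6.3 to +33.7 |
| reads half | 0.906 | 225/(225 + 68.5 + 400) = 0.32 | −20 | −36.2 to −3.8 |

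A simulation of 200,000 pairs gave the same values. With biopsy SD from 10 to 20, r runs from 0.82 to 0.94 through spread alone and does not move with a 20-point offset. Concordance falls from 0.80–0.94 to 0.31–0.64.

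**Precision with up to 34 pairs, in units of the SD of the differences.**

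- Mean difference: 95% CI half-width t(33)/√34 = 2.03/5.83 = 0.35.
- Each limit of agreement: SE = √(1/34 + 1.96²/(2 × 33)) = 0.296, and half-width 2.03 × 0.296 = 0.60.

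Thirty-four is a ceiling. It needs every Group 1 participant to have both a usable MR reading and a biopsy percentage.

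**Why a plain calibration line would mislead.** Suppose MR is perfect, true burden has mean 40% and SD 15 points, and biopsy adds sampling error of SD 10 points (both SDs assumed). Ordinary regression of MR on biopsy then gives slope 225/(225 + 100) = 0.69 and intercept 40 × (1 − 0.69) ≈ 12 points. A test for slope 1 and intercept 0 would fail a perfect tool.

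**The case against.** The strongest objection is that biopsy is not a standard for whole-skeleton burden. Section 3 says so, and a biopsy percentage and an MR percentage can differ even when MR is right. This stands, and it limits what an agreement analysis can claim. It does not rescue correlation, because the same sampling error also lowers r, and r still hides any offset.

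Second, percentage infiltration is a derived measure. The listed tumour-burden endpoint is ADC, in different units, for which correlation with other quantities is reasonable. The study is a pilot with an aim, and section 3's remark about guiding therapy is conditional on feasibility. This stands too. The point concerns one comparison, not the primary ADC analysis. But it is the only planned comparison of MR burden with biopsy on a shared scale, so it bears directly on the word accurately.

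Third, precision is limited and the SD of the differences is unknown. A 95% CI about 1.2 SD wide for each limit is coarse. That is a reason to report the CI, not to leave out the estimate.

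The invariance is exact only for constant and positive proportional errors. A strongly non-linear MR error could change Pearson's r.

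**Conclusion.** The concern holds in a limited form. Section 7.4.1 offers correlation alone for the MR-biopsy pair, section 10.2 does not specify the comparison, and correlation cannot show accuracy. The invariance result needs no assumption about SDs. The concordance figures rest on the assumed biopsy SD of 10 to 20 points and MR error SD of 7. The halving and 20-point errors are illustrations, and nothing in the document says such errors exist.

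A reader might infer more, and the document does not support it:

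- That the study will declare MR accurate because r is high. No section states that conclusion.
- That a difference from biopsy would show the MR percentage to be wrong. Section 3 rules out treating biopsy as the truth for global infiltration.
- That a 20-point error at 40% equals two thirds of the planned fall. That divides an error at one time by a change between two times. Halving would reduce the apparent fall by half, and a constant offset would leave it intact.
- That the primary ADC comparison is undermined. It addresses response, and this point does not touch it.

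**What to change.** In sections 7.4.1 and 10.2, for patients with paired MR and biopsy percentages:

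1. Report the mean MR-minus-biopsy difference with its 95% CI, and a Bland-Altman plot with 95% limits of agreement and their CIs.
2. If differences grow with burden, as a proportional error would produce, use a log or ratio scale or regression-based limits.
3. Keep the correlation coefficient as a secondary description.
4. State that the differences combine MR error with biopsy sampling error and are not MR error alone.
5. Do not test slope 1 and intercept 0 by ordinary regression. If a calibration line is wanted, use an errors-in-variables method, such as Deming regression with a stated error-variance ratio and a sensitivity range, as description only.
6. Keep correlation for pairs in different units, such as FSA against bone mineral density.

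The cost is analysis wording, one plot and a little more analysis, with no new data. The limits may be wide (about ±0.6 SD of the differences each, at best), and the result may look less favourable than r.

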There are a number of widely used modalities that are currently available to visualise bone destruction; including conventional MR (magnetic resonance), whole body low dose CT (WBLDCT) (Pianko *et al*, 2014) and X-ray skeletal survey. However, none of these techniques are quantitative (Marti-Bonmati *et al*, 2015). Of particular note, high-resolution bone volume quantifying CT techniques cannot be used on the central skeleton due to high radiation exposure; although trialled on cortical bone in the peripheral skeleton (Farr *et al*, 2013), this is not the usual site of myeloma bone loss. DXA (Dual-energy X-ray Absorptiometry) scans are widely used in the UK for assessing bone density in patients with osteoporosis but are an insensitive tool in myeloma as it does not show fractures (Marti-Bonmati *et al*, 2015), and therefore are not routinely commissioned for imaging myeloma patients. All of these imaging modalities require significant time and resource commitment over a typical myeloma disease course. Typically a patient may require X rays, PET-CT and spinal MRI within a few weeks for complete staging. If there were a single imaging method that could provide all required quantified staging information this would have both economic and patient convenience benefits.

The use of Magnetic Resonance Imaging (MRI) in Multiple Myeloma has increased dramatically over the last 10 years (Derlin & Bannas, 2014). MRI offers improved detection of lesions in the spine, pelvis, sternum, skull and scapulae as well as exceptional depiction of the spinal cord and nerve roots, detection of soft tissue manifestations and the ability to differentiate between physiological and myeloma-infiltrated bone marrow. Several studies have shown that asymptomatic patients with detectable lesions on MRI have a higher probability to become symptomatic earlier than patients without such lesions. This has therefore been incorporated in the revised IMWG diagnostic criteria (Rajkumar *et al*, 2014).

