8.2 DXA scans

DXA scans will be performed in a 1 hour protocol on the DXA scanner installed at the NOC. Scans will include: body composition, bone mineral density measured at the Lumbar spine (L1-4), hip, whole body and Instant Vertebral Assessment.

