10.2. Analysis of Outcome Measures/Endpoints

Differences in baseline characteristics between participants groups (1, 2 and 3) will be compared using chisquare test for categorical variables and one-way analysis of variance (ANOVA) for continuous variables.

To assess ability of MRI to detect improvement or deterioration in tumour burden and bone health, differences between DW-MRI data imaging from the two time-points (baseline and 6 months follow up) will be tested using paired t test. In addition, ADC, total spine 'hole' and 'collapse' volume and FSA trabecular wall thickness will be compared with bone mineral density at the lumbar spine, total hip and femoral neck T score and g/cm², serum CTX-1 and PINP using correlation analysis in group 1 (complete/very good partial response vs. partial response) and in group 2. These models will be run at baseline and at follow-up.

Differences between groups 1 and 2 in experimental MR measurements at follow up will be estimated using one-way analysis of variance (ANOVA) and analysis of covariance (ANCOVA) when baseline values and potential confounders (including gender, age and body mass index (BMI)) are adjusted. Endpoints will be checked for normality and transformed if possible.

In order to determine the change in EQ-5D throughout the study, repeated measured linear regression analysis will be used where EQ-5D at baseline and follow up will be included as outcome and group as exposure.

Finally, a descriptive analysis of the novel MR imaging scan questionnaire will be conducted to understand participant's experience with the new technique.

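### Collapse volume is correlated only with bone density and turnover markers; the vertebral assessment acquired at the same DXA visits is left out of the analysis

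*Combined protocol and SAP*

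**What the plan says.** Sections 1 and 4 list total spine collapse volume as the third of four novel imaging endpoints under the primary objective. The correlate endpoints there are DXA bone density, serum CTX-1, serum P1NP and further experimental serum biomarkers.

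Section 7.4.1 states that "total spinal lytic and collapse volumes will be correlated with bone mineral density as estimated by DXA scan". Section 10.2 says that the MR measures, collapse volume among them, "will be compared with bone mineral density at the lumbar spine". The same sentence names two hip sites (the femoral neck and the total hip) and adds "serum CTX-1 and PINP using correlation analysis in group 1". Group 2 is analysed as well, and the analyses are run at baseline and at follow-up.

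On DXA itself, section 3 says that such scans "are an insensitive tool in myeloma as it does not show fractures". Section 8.2 lists what the DXA visit acquires: "bone mineral density measured at the Lumbar spine (L1-4), hip, whole body and Instant Vertebral Assessment". Section 7.4.1 lists the same items, section 7.5 repeats them for Groups 1 and 2 at follow-up, and Appendix A shows VFA at both times. Section 13.7 sends the vertebral fracture assessment result to the patient's cancer care team. No other use of it is stated.

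**The concern.** Collapse volume is a new measure; section 3 describes the hole and collapse quantification as entirely novel. Its external support in this study therefore comes from whatever it is correlated with. The planned partners are density at three sites and two turnover markers. They describe how much mineral is present and how fast bone is turning over, not whether a vertebra has lost its shape. The one output of the DXA visit that bears on vertebral shape is acquired twice and then not analysed.

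A second difficulty applies to lumbar density only. Areal density is mineral divided by projected area. Low density predisposes to collapse, which pushes the correlation negative. Collapse shrinks the area, which pushes measured lumbar density up and the correlation positive. A weak lumbar correlation would then be hard to read: it could reflect a poor MR measure or two opposing effects. The same shift affects lumbar density when it is the comparator for hole volume and FSA.

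**Working it through.** **1. What each planned comparator can show about collapse**

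- Lumbar density (g/cm² and T score): does not measure vertebral shape, and is itself altered by collapse.
- Total hip and femoral neck density: does not measure vertebral shape, and is not altered by vertebral collapse.
- CTX-1 and PINP: turnover markers, not structural.
- IVA/VFA: section 13.7 calls it a vertebral fracture assessment, so it bears directly on collapse. It is absent from section 4, from the correlations in 7.4.1 and from 10.2.

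The within-visit repeats in section 7.4.1, offered because there is no gold standard for myeloma bone loss, cover MR bone density measurements only. Collapse volume thus has no matched structural comparator and no stated within-visit repeat.

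**2. Size of the effect on lumbar density**

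The plan states no figure on this point, so there is none to reproduce. Inputs: the measured region is L1-4, four levels (sections 7.4.1 and 8.2). Assumptions: levels of equal area and mineral, constant mineral and width, and illustrative height losses of 25% and 40%. The documents give no height losses.

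For a single level, the density ratio is 1/(1 − h), where h is the fraction of height lost:
- h = 0.25: 1/0.75 = 1.33
- h = 0.40: 1/0.60 = 1.67

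The planned quantity is the lumbar region, so the pooled ratio applies. With k levels collapsed it is 4/(4 − k·h):
- k = 1, h = 0.25: 4/3.75 = 1.067, a rise of about 7%
- k = 1, h = 0.40: 4/3.60 = 1.111, a rise of about 11%
- k = 2, h = 0.25: 4/3.50 = 1.143, a rise of about 14%
- k = 2, h = 0.40: 4/3.20 = 1.25, a rise of 25%

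If the collapsed level also loses a fraction m of its mineral, the ratio for k = 1 is (4 − m)/(4 − h). At m = h the rise vanishes: with both at 0.25, 3.75/3.75 = 1. The direction is therefore not fixed. Section 3 describes lytic lesions and trabecular thinning alongside collapse, so some mineral loss is plausible.

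**3. Precision of any correlation**

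Approximate 95% interval: tanh(atanh(r) ± 1.96/√(n − 3)), with an assumed true r of 0.3:
- n = 34 (Group 1): −0.04 to 0.58
- n = 29 (complete or very good partial response, section 10.1): −0.07 to 0.60
- n = 13 (Group 2): −0.30 to 0.73
- n = 5 (partial response, section 10.1): −0.79 to 0.93

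**The case against.** The strongest reply is that this is an exploratory pilot. The plan says correlated and compared, section 7.4.1 concedes that no gold standard exists, and no decision rule rests on the result. Section 10.1 names ADC as the primary outcome and sizes the study on it. At these sample sizes, no comparator would settle how well collapse volume performs. All of this stands, and it limits the weight of the point. It does not explain why the closest available comparator is left out.

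A reader might infer that the plan validates collapse volume against bone density, so that a weak correlation would fail the measure. The documents do not say so. A reader might also infer that every planned density correlation is distorted. That is wrong as well: hip and femoral neck density are in section 10.2 and are untouched by vertebral collapse. The single-level rises of 33% and 67% should not be read as the effect on the planned lumbar measure, which pools four levels.

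Three further points count against simply replacing density with IVA:
- The documents do not say what IVA reports, and a count or grade is not a volume.
- Section 7.1 describes Group 2 as without X-ray detectable bone disease, so a correlation there may be uninformative.
- Dropping collapsed levels as a rule would lose lumbar data in the worst-affected patients and could change the level set between visits.

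These points shape the fix but do not remove the need for it.

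Finally, fracture history and vertebral augmentation are recorded at screening (section 7.3.2), and relevant NHS results are collected (section 5). Neither is named in section 10.2 as a comparator.

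**Conclusion.** The point holds as a cheap improvement. A listed primary imaging endpoint is correlated only with quantities that do not measure vertebral collapse, while a better matched result from the same DXA visits has no place in the analysis. It is fair to say that IVA/VFA is unused in the written analysis. To say that it is unused altogether would be wrong, because section 13.7 gives it a clinical use.

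The lumbar area effect is secondary. It is about 7% to 11% for one collapsed level under constant mineral and width, more with several collapsed levels, and less or nothing if mineral is lost. It does not reach the hip or femoral neck.

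The conclusion assumes that IVA in sections 7.4.1 and 8.2, VFA in Appendix A and the vertebral fracture assessment in section 13.7 are the same examination. It also assumes that its report gives at least the presence of fracture by level. The documents do not give the frequency of collapse in this cohort.

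**What to change.** - **Sections 4, 7.4.1 and 10.2:** add the IVA/VFA result (vertebral fracture presence, number or grade, as reported) as the main structural comparator for collapse volume at both visits. Limit it to levels covered by both methods, and state which these are: section 3 describes 3D imaging of spine and pelvis, section 7.4.1 of pelvis and lumbar spine.
- **Method:** rank correlation in Group 1; description only in Group 2, where few or no fractures are expected.
- **Existing correlations:** keep density at all three sites, CTX-1 and PINP as further correlates.
- **Sensitivity analysis:** repeat the lumbar density correlations for hole volume and FSA without levels flagged on IVA, using the same level set at both visits.

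Cost: amended wording and a little more analysis. No extra scan, visit or radiation exposure is needed. The sensitivity analysis will use less lumbar data, by an amount that the documents do not allow to be estimated.
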